10.3 Analysis Datasets

The statistical analyses will be performed only when the data have been declared clean and the study database has been locked.

10.4 Description of Statistical Methods

All data on a continuous scale will be presented using box plots with individual data points overlaid. To examine treatment effects and to test the hypothesis of no differences in the mean between baseline, week 1 and week 4 the Wilcoxon signed-rank test will be calculated for the differences in data distributions (change over time) from baseline (day 0) to week 1 and to week 4 (follow-up 4). The Wilcoxon signed-rank test is a non-parametric test and does not require the data to follow a particular distribution; it is robust to single gross outliers and has higher power than a t-test, unless the data follow exactly a Gaussian distribution, and then the power is very close.

For test of the hypothesis of at least 25% reduction of seizures, the Wilcoxon signed rank test and associated point estimate and 2-sided 95% confidence intervals will be calculated on the log transformed data. We will conclude a 25% reduction of seizures if the upper confidence limit is lower or equal than 0.75 on the original scale.

All tests of statistical hypotheses will be done on the two-sided 5% level of significance and presented together with the associated point estimate and two-sided 95% confidence interval. Since this is an initial proof-of-concept study that is exploratory in nature, no multiplicity-related adjustments will be made in the reported p-values.

The SAS software, proc npar1way or similar R software package will be used to perform the statistical analyses.

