Statistical Methods:	Safety and tolerability aspects of the data will be tabulated. An adverse event (AE) will be defined as any untoward medical occurrence in a study subject, temporally associated with the use of the experimental medication, whether or not considered related to the medication. An

	 adverse event can therefore be any unfavorable and unintended sign (including an abnormal laboratory finding), symptom, or disease (new or exacerbated) temporally associated with the use of the experimental medication. A serious adverse event (SAE) will be defined as an AE that meets any of the following criteria: results in death; is life threatening; requires inpatient hospitalization; results in a persistent or significant disability/incapacity; any other adverse event that, based upon appropriate medical judgment, may jeopardize the subject's health and may require medical or surgical intervention to prevent one of the outcomes listed above
	For the assessment of efficacy, to test the hypothesis of no differences in the mean between baseline, week 1, and week 4 we will examine the data distributions of the primary and secondary efficacy variables. The primary analysis and study evaluation will be based on the 10 subjects recruited for this study. All tests of statistical hypothesis will be done on the two-sided 5% level of significance and presented together with the associated point estimate and two-sided 95% confidence interval.
	Since the study participants are expected to have very differing degrees of baseline signs and symptoms, the evaluation of treatment effects will include an adjustment for the pre-treatment baseline level in each treatment period. For this purpose, the differences against baseline will be analysed.
	Since this is an initial proof-of-concept study that is exploratory in nature, no multiplicity-related adjustments will be made in the reported p-values.
	The SAS software, proc npar1way or similar R software will be used to fit the statistical models.
Phase:	Phase IIa
Number of Sites enrolling participants:	2
Description of Study Agent:	AMO-01 (INN: diazepinomicin), formerly known as ECO-4601 and TLN-4601, is a low molecular weight, brain penetrating, structurally novel, farnesylated dibenzodiazepinone.

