Urinalysis	X	Х		Х	X	X	
Pregnancy Test ³	X	Х		X	X	X	
Sample for Pharmacokinetic		X					
Analysis ⁴		Λ					
Sample for Assessment of		Х		X		X	
Phosphorylated ERK levels ⁵				Λ		Λ	
Administer Study Medication ⁶		Х					
Seizure Diary Dispense/Review	X	Х		Χ	Х	Х	
CGI-S	X	Х		X	Х	X	
CGI-I		Х		Χ	Х	X	
Clinician Completed PMS	X	Х		X	X	X	
Domain Specific Causes for	Λ	Λ		Λ	Λ	Λ	
Concern VAS							
Sensory Adjustment for							
Neurodevelopmental Disorders		X		Х	X	X	
(SAND)							
Caregiver Top 3 Concerns		Х		X	X	X	
Aberrant Behavior Checklist		Х		X	X	X	
(ABC)							
Repetitive Behavior Scale-		Х		X	X	X	
Revised (RBS-R)							
Electroencephalography	X		X	X	X		
Computerized eye tracking	X	Х	X	X	X	X	
Auditory Evoked Potential	X	Х	X	X		X	

Visual Evoked Potential	X	Х	X	X		X	
Adverse Events ⁷	X	X		X	X	X	X
Concomitant Medications	X	Х		X	X	X	X
Telephone questionnaire							X

- 1. Vital Sign Measures include Heart Rate, Respiratory Rate, Blood Pressure, Temperature, Height, and Weight
- 2. Clinical labs standardly include i) Full Blood Count with differential, ii) Biochemistry panel. When marked with an "a", a lipid panel will also be collected
- 3. Urine or serum pregnancy test for female subjects of child bearing potential
- 4. Pharmacokinetic sample (6 mL) will be taken at approximately 2 hours and approximately 6 hours after the start of the infusion as well as 1 hour after the cessation of the study drug.
- 5. 6 mL blood sample required for assessment of phosphorylated ERK levels
- 6. A single 6-hour intravenous treatment will be given to subjects, with total dose administered 120 mg/m²
- 7. Adverse Events (AEs) and Serious Adverse Events (SAE's) will be collected from the time of informed consent.
- 8. Baseline procedures outlined in Table 2, Baseline Visit Schedule of Events

Table 2: Baseline Visit Schedule of Events

Baseline Procedures	Pre-Infusion ¹⁰	During Infusion	Post-Infusion ⁹
V2			
Week 0			
Eligibility Criteria	Х		
Physical Examination ¹	Х	X	X ^a
Vital Sign Measures ²	Xb	X	X
ECG	Х	X ³	
Clinical Labs ⁴	X		
Urinalysis	Х		
Pregnancy Test ⁵	Х		
Sample for Pharmacokinetic Analysis ⁶	X	Х	X
Sample for Assessment of Phosphorylated ERK levels ⁷	X	X	
Administer Study Medication ⁸		X	
Seizure Diary Dispense/Review	Х		
CGI-S	Х		
CGI-I			X
Clinician Completed PMS Domain Specific Causes for Concern VAS	X		
Sensory Adjustment for Neurodevelopmental Disorders (SAND)	X		
Caregiver Top 3 Concerns	Х		
Aberrant Behavior Checklist (ABC)	Х		

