Repetitive Behavior Scale- Revised (RBS-R)	Х		
Electroencephalography			
Computerized eye tracking	X		
Auditory Evoked Potential	X		
Visual Evoked Potential	X		X
Adverse Events	X	Х	X
Concomitant Medications	X	Х	X

1. When marked with a) a brief physical examination is acceptable

2. Vital Sign Measures include Heart Rate, Respiratory Rate, Blood Pressure, Temperature. When marked with b) Height, and Weight are also measured

3. ECG during infusion to be completed between 4-6 hours after infusion start

4. Clinical labs standardly include i) Full Blood Count with differential, ii) Biochemistry panel

5. Urine or serum pregnancy test is sufficient

6. Pharmacokinetic sample (6 mL) will be taken pre-infusion and at approximately 2 hours and approximately 6 hours after the start of the infusion as well as 1 hour after the cessation of the study drug.

- 7. 6 mL blood sample required for assessment of phosphorylated ERK levels will be taken pre-infusion and at approximately 2 hours and approximately 6 hours after the start of the infusion as well as 1 hour after the cessation of the study drug.
- 8. A single 6-hour intravenous treatment will be given to subjects, with total dose administered 120 mg/m^2
- 9. Post-infusion assessments will occur one hour after infusion prior to discharge with the exception of EEG which occurs the following day in the AM
- 10. If required for scheduling, pre-infusion assessments can be completed one day prior to the infusion

ii. Table of Contents

i. I	Protocol Synopsis	4
ii.	Table of Contents	14
LIS	ST OF ABBREVIATION	19
iii.	. Table of Tables	20
iv.	SCHEMATIC OF STUDY DESIGN	20
1.	KEY ROLES	21
2.	INTRODUCTION: BACKGROUND INFORMATION AND SCIENTIFIC RATIONALE	23
,	2.1 Background Information	23
	2.1.1 Phelan McDermid Syndrome (PMS)	23
,	2.1.2 AMO-01 and Rationale for Clinical Investigation	23
,	2.1.3 Pre-Clinical Research	25
2.1	1.4 Non-Clinical Pharmacology	25
2.1	1.5 Non-Clinical Pharmacokinetics, Metabolism and Interactions	26
2.1	1.6 Non-Clinical Toxicology	27
2.1	1.7 Clinical Experience	28
2.1	1.8 Safety Summary	28
2.2	2 Rationale	29
2.3	3 Potential Risks and Benefits:	33
3.	OBJECTIVES AND PURPOSE	34
4.	Study Design and Endpoints	34
4	4.1 Description of the Study Design	34
4	4.2 Study Endpoints	35
	4.2.1 Primary Endpoint:	35
	4.2.2 Secondary Endpoints:	35
4	4.2.3 Exploratory Endpoints:	35
5.	Study Enrollment and Withdrawal	36
	5.1 Participant Inclusion Criteria	36
	5.2 Participant Exclusion Criteria	36

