2.1.5 Non-Clinical Pharmacokinetics, Metabolism and Interactions

Absorption, Distribution, Metabolism and Excretion (ADME) studies in mice, rats, and monkeys have shown distribution of AMO-01 in several organs and elimination in urine and feces. Human microsome stability of AMO-01 was studied, as well as its metabolism *in vitro* in hepatocytes from several species. Metabolite identification was also performed in mice, rats, and monkeys. A simulation of the pharmacokinetic profile of

AMO-01 in humans is presented from data generated in several species following IV bolus or continuous IV infusion.

In mouse studies, the presence of measurable quantities of AMO-01 in brain tissue suggests that the drug crosses the blood-brain barrier. In all species, a single IV bolus injection of AMO-01 resulted in a high C_{max} and a subsequent rapid elimination from the plasma (less than 4 hours in monkeys). Effective *in vitro* concentrations for Ras-ERK pathway inhibition were in the range of 1 to 10 μ M, and were similar to the 2 μ M target concentration threshold identified for the previous cancer indication. The rapid clearance after IV bolus administration prevented sustained concentrations above the target concentration threshold; therefore, subsequent 7- and 14- day continuous infusions dose studies were conducted in rat and monkey, and infusions were also used in the clinical oncology program. An analysis was performed to derive allometric equations for AMO-01 pharmacokinetic parameters using AMO-01 plasma concentration-time data from three species, including mouse, rat, and monkey, and to estimate human pharmacokinetic parameters from those allometric equations can be found in the Investigator's Brochure.

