4.2 Study Endpoints

4.2.1 Primary Endpoint:

- The incidence of Adverse Events (AEs) including Serious Adverse Events (SAEs) between Baseline and Week 8.
- The incidence of abnormal findings in objective assessments (e.g. laboratory values, ECGs, vital signs)

4.2.2 Secondary Endpoints:

- Seizure frequency as measured by a caregiver-completed seizure diary
- Syndrome-specific Clinical Global Impressions Improvement Scale (CGI-I)
- Clinician-completed PMS domain specific causes for concerns visual analogue scale (VAS)
- Top 3 caregiver Concerns VAS
- Aberrant Behavior Checklist (ABC) score
- Repetitive Behavior Scale- Revised (RBS-R) score
- Eye-tracking time on relevant target
- Change in phosphorylated ERK levels
- Telephone follow-up questionnaire

4.2.3 Exploratory Endpoints:

- Sensory Assessment for Neurodevelopmental Disorders (SAND)
- Electroencephalography (EEG)
- Auditory Evoked Potential (AEP)
- Visual Evoked Potential (VEP)

5. Study Enrollment and Withdrawal

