7.2.2.3 Change in phosphorylated ERK levels

Samples of 6 ml blood will be taken pre-infusion, approximately 2 and 6 hours after the start of the infusion, approximately 1 hour after the cessation of the infusion, and at the 1 week (V4) and 4 week (V6) visits. The sample will be provided as whole blood with fixative, to be used for the analysis of levels of phosphorylated ERK and total ERK protein.

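### The only planned tests of pERK change fall at Weeks 1 and 4; the samples drawn during and just after the 6-hour infusion have no pre-specified test or interval

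*Combined protocol and SAP*

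**What the plan says.** **Endpoint and sampling.** Protocol section 4.2.2 lists "Change in phosphorylated ERK levels" as a secondary endpoint and attaches no timepoint to it. Section 7.2.2.3 calls for a pre-infusion sample, then samples "approximately 2 and 6 hours after the start of the infusion, approximately 1 hour after the cessation of the infusion", then samples at Weeks 1 and 4. Both pERK and total ERK are assayed.

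**Inference.** Section 10.4 applies the Wilcoxon signed-rank test to "change over time) from baseline (day 0) to week 1 and to week 4 (follow-up 4". The Statistical Methods part of the synopsis uses the same times: "to test the hypothesis of no differences in the mean between baseline, week 1, and week 4". Neither text names pERK, and neither exempts it. Section 10.4.3, on the secondary endpoints, deals only with seizure frequency. The hypotheses in section 10.2 cover safety, seizures and EEG. No section gives pERK its own test, key timepoint or scale.

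**Description.** Section 10.4 plans box plots showing individual values for all continuous data. Section 10.4.1 makes summary statistics and graphs, with baseline subtracted, the main form of analysis. Section 10.4.10 promises listings of all individual data. Section 10.1 leaves the details to a separate SAP, to be completed before database lock.

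**Pharmacokinetics.** After an IV bolus in animals, section 2.1.5 reports a high peak and "subsequent rapid elimination from the plasma (less than 4 hours in monkeys". It gives this rapid clearance as the reason for moving to infusions.

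**Schedule.** In Table 2 the row "Sample for Assessment of Phosphorylated ERK levels" is marked before and during infusion only. Footnote 7 to that row says that a "blood sample required for assessment of phosphorylated ERK levels will be taken pre-infusion and at approximately 2 hours and approximately 6 hours", and adds a sample 1 hour after the drug is stopped.

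**The concern.** Of the listed endpoints, pERK is the one that can show whether this dose inhibits the pathway on which the rationale rests. The plan collects five post-baseline samples but tests only the last two, both long after a single infusion of a drug described as rapidly cleared. The three samples taken when drug is present, or has only just stopped, get no test. Section 10.4 attaches point estimates and 95% intervals to tests, so they get no interval either.

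At stake is how the mechanism result is read. If the clinical endpoints are flat and pERK is null at Weeks 1 and 4, it is easy to conclude that the target was missed, although inhibition and recovery would give the same two p-values. If the clinical endpoints improve, there is no pre-specified engagement result to set beside them. A further point is that the Table 2 grid and its own footnote disagree on whether the post-infusion sample is taken.

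**Working it through.** The documents give no power or effect-size figure for pERK to reproduce; section 10.5 says the sample size had no statistical basis. Two illustrative checks follow.

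**1. Drug remaining at the tested visits**

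Inputs:
- Level during infusion: about 5.9 µM (section 2.2.1, the plan's projection).
- In vitro range for Ras inhibition: 1 to 10 µM, with an overall minimum effective level of about 3 µM (section 2.2.1).
- Infusion length: 6 h.
- Time after the end of infusion: Week 1 is 7 × 24 − 6 = 162 h; Week 4 is 28 × 24 − 6 = 666 h.
- Half-life: an assumption, because no human value is given. The range tried is 4 to 72 h.

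Formula (one-compartment decay): C = 5.9 × 2^(−t / half-life).

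| Assumed half-life | Week 1 (µM) | Week 4 (µM) |
|---|---|---|
| 4 h | 3.8 × 10⁻¹² | 4.5 × 10⁻⁵⁰ |
| 12 h | 0.0005 | 1.2 × 10⁻¹⁶ |
| 24 h | 0.055 | 2.6 × 10⁻⁸ |
| 48 h | 0.57 | 0.0004 |
| 72 h | 1.24 | 0.0097 |

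Half-life needed to remain at a threshold = t / log2(5.9 / threshold):
- 1 µM: 162 / 2.561 = 63 h for Week 1; 666 / 2.561 = 260 h for Week 4.
- 3 µM: 162 / 0.976 = 166 h for Week 1; 666 / 0.976 = 683 h for Week 4.

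**2. What the same test could do on the infusion day**

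Exact two-sided signed-rank test at 5%, simulated with 200,000 runs and normally distributed differences. The standardised changes are assumptions. The plan expects up to 10 treated subjects. Seven is shown because section 10.2 hypothesises that at least 70% complete the infusion.

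| Assumed true change | n = 10 (attained alpha 0.0488) | n = 7 (attained alpha 0.0469) |
|---|---|---|
| 0 SD | 5% | 5% |
| 0.25 SD | 11% | 8% |
| 0.8 SD | 60% | 40% |
| 1.0 SD | 79% | 57% |
| 1.5 SD | 98% | 88% |

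If pERK is back at baseline by Week 1, each planned test rejects only about 5% of the time, whatever the size of the earlier inhibition. On the infusion day, the same test with 10 subjects would have reasonable power for a change of 1 SD or more.

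**The case against.** The strongest reply is that nothing is hidden. The values from during and just after infusion would appear in box plots, change-from-baseline summaries and listings, and description is the plan's stated main mode of analysis. A reader might infer that real inhibition would be reported as no effect, or that the study could not tell non-inhibition from inhibition followed by recovery. The documents support neither. In at most 10 people, a fall at 6 h with a return by Week 1 would be visible subject by subject. What is missing is a pre-specified test, interval and key timepoint.

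Second, plasma drug is not pERK effect. The elimination data come from animals given an IV bolus, and no pERK recovery time is given. Section 2.1.4 reports mouse behavioural effects lasting at least five days after one dose. Those data are not pERK and stop short of Week 1, so they neither show nor exclude persistence. They do make Week 1 a sensible persistence check. This stands: the arithmetic does not prove that pERK will be null at Week 1, and a half-life near 72 h would leave more than 1 µM there, although that fits poorly with rapid elimination.

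Third, the separate SAP could add a test. It could, but the protocol already fixes Weeks 1 and 4 as the tested times, and in an open-label study a pERK timepoint chosen after values have been seen carries less weight.

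On Table 2, a reader might infer that sites will miss the post-infusion sample. That goes too far: footnote 7 belongs to that row and requires the sample, section 7.2.2.3 agrees, and PK blood is drawn at the same time. What remains is an inconsistency to tidy.

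**Conclusion.** The point holds as a matter of timing and pre-specification. Three of the five post-baseline pERK samples, including every one taken with drug present or just stopped, have no planned test or interval. The two that do fall about 162 h and 666 h after the infusion. For assumed half-lives of 4 to 24 h, the residual at Week 1 is at most about 0.06 µM against a 1 µM lower end of the active range.

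This rests on three things: the general rule in section 10.4 applies to pERK, since no other rule does; human elimination is rapid in the sense that section 2.1.5 describes for animals; and a one-compartment decay is an adequate guide. The conclusion is limited to this: the planned tests are poorly placed to detect transient inhibition, and null results at Weeks 1 and 4 would not be evidence that the pathway was not engaged.

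**What to change.** In section 10.4.3 and the SAP, before any pERK data are examined:

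- Name the pERK measure, for example the ratio of pERK to total ERK, and say whether change is a difference or a log ratio.
- Name one infusion-day comparison with the pre-infusion sample, for example about 6 h (end of infusion), using the same signed-rank test, point estimate and 95% interval. The sample 1 hour after infusion would also be defensible; what matters is choosing one in advance.
- Treat the other infusion-day samples as supportive, and label Weeks 1 and 4 as tests of persistence.
- State that a null result at Weeks 1 and 4 alone will not be interpreted as lack of engagement.
- Reconcile the Table 2 pERK row with footnote 7 and section 7.2.2.3.

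The cost is a short paragraph and one table cell, with no new samples, visits or assays. The downside is a few more unadjusted p-values in a study that already makes no multiplicity adjustment.

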10.4.1 General Approach

The safety and efficacy data will primarily be analyzed using summary statistics (number of values, number of missing values, mean, median, standard deviation, 1st and 3rd quartiles and minimum and maximum values) and graphs. Since the study participants are expected to have widely differing degrees of baseline signs and symptoms, the evaluation of treatment effects will include an adjustment for the baseline level by subtracting the baseline data from measurements post baseline.

10.4.2 Analysis of the Primary Endpoint(s)

Adverse events (AEs) will be tabulated. Changes in rates of particular groups of AEs from baseline to follow-up may be formally examined calculating the McNemar test.

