AMO-01 is a Ras-ERK pathway inhibitor, and may also have potential therapeutic utility as an anticonvulsant. The Ras-ERK pathway has been implicated in seizure generation according to a number of converging lines of evidence in different experimental models, and in the use of Ras-ERK pathway inhibitors. Aberrations in the genes that regulate the activity of the MAPK/ERK pathway are also strongly associated with neurodevelopmental disorders including autism (Wen et al., 2016; Garg et al., 2017; Tylee et al., 2017). Further, it is known that SHANK3 sequesters the Ras enzymatic protein, thereby modulating its activity (Lilja et al., 2017), and it has been shown that ERK activity is increased at least threefold in the cortex of Shank3b --- knockout mice (AMO Pharma Internal Report AMO-01-PC-001). Importantly, administration of AMO-01 to the Shank3b -/- knockout model of PMS reversed behavioral abnormalities in these mice and reduced seizure activity after a single dose. Therefore, AMO-01 may provide benefit to

	PMS patients exhibiting behavioral abnormalities and seizures.
Study Design:	This is an open-label study to investigate the safety, tolerability and efficacy of a single 6-hour intravenous infusion of AMO-01 to treat adolescents and adults with PMS and co-morbid epilepsy.
	The subjects in this study will be administered the experimental study medication and then be followed up to ascertain safety and tolerability, and to determine whether their seizure frequency, as well as their signs and symptoms of PMS, are improving, using a caregiver-completed seizure diary as well as accepted rating scales and functional measures. In addition, pre- and post-treatment clinical EEGs will be obtained to determine whether AMO-01 diminished the prevalence of abnormal EEG findings that were evident prior to treatment. Approximately 15 subjects will be screened and up to 10 subjects will receive study medication.
	 The study will have 4 phases: Screening (Weeks -4 to -1): Subjects will be screened to ensure adherence to eligibility criteria and to assess pre-medication seizure frequency Baseline (Day 0): Subjects will complete baseline assessments in-clinic prior to study drug administration Study Drug Administration (Day 0): Eligible subjects will receive a single 6-hour intravenous infusion at a single dose of 120 mg/m² Follow-up (Weeks 0-4): follow-up visits will occur at 1 day after and 1, 2, 4, and 8 weeks after receiving study medication.

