7.3 Study Schedule

7.3.1 Screening

The Screening visit (V1) will occur in the 4 weeks preceding the Baseline visit (V2). Participants and their families will come in to sign the informed consent and meet with members of the study team. Refer to the schedule of events (Table 1) for the assessments to occur at the Screening visit (V1).

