8 ASSESSMENT OF SAFETY

8.1 Specification of Safety Parameters

8.1.1 Definition of Adverse Events (AE)

An adverse event (AE) will be defined as any untoward medical occurrence in a study subject, temporally associated with the use of the experimental medication, whether or not considered related to the medication. An adverse event can therefore be any unfavorable and unintended sign (including an abnormal laboratory finding), symptom, or disease (new or exacerbated) temporally associated with the use of the experimental medication.

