8.3 Time Period and Frequency for Event Assessment and Follow-Up

All AEs occurring from screening (V1) until the time of the follow-up phone call 8 weeks after study drug administration will be recorded on the Adverse Event form in the subject's CRF, irrespective of severity or whether or not they are considered medication-related. Onset of chronic illness (e.g. autoimmune disorders, asthma, type 1 diabetes and allergies) and conditions prompting emergency room (ER) visits or physician office visits that are not related to well-child care, injury, or common acute illnesses (e.g., upper respiratory tract infection, otitis media, pharyngitis, and gastroenteritis) will be reported during the entire study period. The investigator will inquire about the occurrence of AEs at every visit/contact during the study and throughout the follow-up phase as appropriate. All AEs either observed by the investigator or a clinical collaborator or reported by the subject's parent/guardian spontaneously or in response to a direct question will be evaluated by the investigator. AEs not previously documented in the study will be recorded in the Adverse Event form within the subject's CRF. The nature of each event, date and time (where appropriate) of onset, outcome, intensity and relationship to drug administration should be established. Details of any corrective treatment should be recorded on the appropriate page of the CRF.

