10.4.4 Safety Analyses

See Analysis of Primary Endpoint (Section 10.4.2)

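### The optional McNemar test of adverse events has no defined windows, and on the unequal collection periods the protocol describes it leans toward a false rise

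*Combined protocol and SAP*

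**What the plan says.** Section 10.4.2, on the primary endpoint, provides for tabulation of AEs and then one optional test: "Changes in rates of particular groups of AEs from baseline to follow-up may be formally examined calculating the McNemar test". Section 10.4.4, on safety analyses, only refers back to 10.4.2, so this is the only formal test named for AEs. Neither section says what period counts as baseline or follow-up, which AE groups are meant, or whether the exact or a chi-square version would be used.

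The AE periods have to be read from other places:

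- Start of collection (synopsis, Table 1, footnote 7): "Adverse Events (AEs) and Serious Adverse Events (SAE's) will be collected from the time of informed consent".
- Timing of consent (synopsis, Study Design): "Screening (Weeks -4 to -1): Subjects will be screened to ensure adherence to eligibility criteria". Section 7.3.1 places the Screening visit within the 4 weeks before Baseline and sets no minimum gap.
- Extent of collection (Section 8.3): "All AEs occurring from screening (V1) until the time of the follow-up phone call 8 weeks after study drug administration".
- Endpoint (Section 4.2.1): "The incidence of Adverse Events (AEs) including Serious Adverse Events (SAEs) between Baseline and Week 8".

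Section 10.4.1 says safety data are analysed primarily with summary statistics and graphs. Section 10.1 leaves all analysis details to a separate SAP, to be finalised before database lock.

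**The concern.** McNemar's test compares the number of subjects with an event only after dosing with the number who had one only before. It speaks to a drug effect only if the two periods give the same opportunity for events. The periods described here differ by a factor of 2 (8/4) to 8 (8/1), and the factor varies by subject. A longer observation period collects more first events, so a subject is more likely to fall in the after-only cell with no drug effect at all.

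At stake is a p-value, at the two-sided 5% level and without multiplicity adjustment (Sections 10.4 and 10.4.9), that could be reported as evidence that AEs increased after the infusion. Because the AE groups are not named, they could also be chosen after the data have been seen.

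**Working it through.** The plan gives no event rate, power or error rate for this test, so there is no figure to reproduce.

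**Inputs from the protocol.** Up to 10 subjects dosed (Section 4.1); two-sided 5% level (Section 10.4); pre-dose window w of 1 to 4 weeks (synopsis); post-dose window of 8 weeks (Sections 4.2.1 and 8.3).

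**Assumptions, not in the protocol.** A constant AE rate r per subject-week, identical before and after dosing (no drug effect), the same in all subjects, and independent over time. The range shown is r = 0.05 to 0.3.

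**Step 1: cell probabilities.** The chance of at least one AE in t weeks is 1 − exp(−rt). Therefore

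- P(after only) = (1 − exp(−8r)) × exp(−rw)
- P(before only) = (1 − exp(−rw)) × exp(−8r)

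For r = 0.1:

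- w = 1: after only = 0.551 × 0.905 = 0.498; before only = 0.095 × 0.449 = 0.043.
- w = 4: after only = 0.551 × 0.670 = 0.369; before only = 0.330 × 0.449 = 0.148.

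A valid null comparison would have the two probabilities equal.

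**Step 2: rejection region.** Let b be the after-only count and c the before-only count. The exact two-sided p-value comes from the binomial distribution with b + c trials and probability 0.5. A split of 5:0 gives p = 0.0625 and 6:0 gives p = 0.031, so fewer than six discordant subjects can never reach significance. The uncorrected chi-square, (b − c)²/(b + c), already rejects at 4:0 (p = 0.0455). The continuity-corrected version gave the same rejection rates as the exact test in every scenario run with 10 subjects.

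**Step 3: chance of a significant rise.** Sum the trinomial probabilities for 10 subjects over all (b, c) with b > c and p ≤ 0.05. The nominal value in this one direction is 2.5%.

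| Pre vs post (weeks) | Test | r = 0.05 | r = 0.1 | r = 0.2 | r = 0.3 |
|---|---|---|---|---|---|
| 1 vs 8 | exact | 4.9% | 28% | 60% | 69% |
| 1 vs 8 | uncorrected | 30% | 59% | 78% | 86% |
| 2 vs 8 | exact | 3.3% | 16% | 30% | 29% |
| 2 vs 8 | uncorrected | 21% | 38% | 53% | 60% |
| 4 vs 8 | exact | 1.5% | 4.8% | 5.5% | 2.2% |
| 4 vs 8 | uncorrected | 10% | 15% | 20% | 17% |
| 4 vs 4 | exact | 0.06% | 0.3% | 0.4% | 0.3% |
| 4 vs 4 | uncorrected | 1.6% | 2.6% | 2.6% | 2.5% |

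On a grid of r from 0.01 to 1.99, the maximum for 4 vs 8 weeks is 6.1% exact and 20.5% uncorrected. For 4 vs 4 weeks it is 0.45% and 2.6%. Equal windows therefore remove the inflation.

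**Step 4: sensitivity.**

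- *Rare AE groups.* At r = 0.02 with 1 vs 8 weeks, the exact test gives 0.1%.
- *Mixed windows.* With pre-dose windows spread evenly over 1 to 4 weeks and the same four rates, the exact test gives 3% to 22%.
- *Subjects with different rates* (gamma-distributed with shape 1, an assumption). Mixed windows then give 1% to 7% exact and 12% to 31% uncorrected; a 1-week window gives 2% to 32% exact.

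**The case against.** The strongest reply is that nothing says the test would be run on these periods. Section 10.4.2 leaves the windows open, visit-level comparisons are possible, and Section 10.1 defers details to a separate SAP. That stands: the defect in the text is that the windows are undefined, and the 1-to-4 against 8-week contrast is inferred from the collection periods. It does not remove the concern, because no other AE periods are described. Carrying over the general baseline rule of Section 10.1 (the measurement closest before dosing) would shorten the pre-dose side further.

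The second reply is that the test hardly matters. It is optional, tabulation comes first, the safety hypothesis in Section 10.2 concerns absence of SAEs and completion of the infusion, and the halting rules in Sections 5.5 and 8.5 do not use it. This also stands. A reader might infer that the analysis of the primary objective is biased as a whole; the documents do not support that. The bias described runs toward a false alarm.

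Third, the large percentages need short pre-dose windows and common events. With a full 4 weeks and the exact test, inflation is slight, and named AE groups will be rarer than AEs overall. That is correct, but the plan guarantees neither a 4-week window nor the exact version.

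Finally, a reader might infer from Section 8.1.1, which defines an AE as "temporally associated with the use of the experimental medication", that pre-dose events would go uncounted and the imbalance would grow. The documents do not support this: Table 1 footnote 7, Section 7.1.5 and Section 8.3 all call for collection from consent or screening, and Section 8.3 does so regardless of relatedness.

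**Conclusion.** The concern holds in limited form. The optional test is under-specified, and on the only AE periods described it is biased toward a rise with no drug effect. At the four assumed rates, the false-rise probability is 5% to 69% (exact) or 30% to 86% (uncorrected) if every subject has a 1-week pre-dose window, and 1.5% to 5.5% or 10% to 20% if every subject has 4 weeks, against a nominal 2.5%. These figures rest on 10 subjects, constant and equal rates, and independent events; differences between subjects reduce them but do not remove the inflation for short windows or the uncorrected test. The consequence is confined to a potentially misleading safety p-value. It is worth correcting because correction costs almost nothing.

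**What to change.** Preferred: delete the McNemar sentence. Report treatment-emergent AEs as the number and proportion of subjects with at least one event, with exact 95% confidence intervals.

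If a before-after comparison is kept, name the AE groups in the SAP before database lock and choose one of these:

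- **Person-time.** Report events per person-week before and after dosing, with a rate ratio and an exact conditional Poisson 95% CI that uses each subject's own pre- and post-dose time. With no drug effect, a subject observed for 1 and 8 weeks is expected to have 8/9 = 89% of events after dosing, and one observed for 4 and 8 weeks 8/12 = 67%; the method allows for this.
- **Equal windows.** Cut each subject's post-dose window to the length of that subject's pre-dose window and use the exact McNemar test.

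Do not specify a fixed 28-day pre-dose window: AEs are collected only from consent, so subjects screened later would not have 28 days of data.

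The cost is SAP wording, with no added visits or data. The equal-window version leaves later post-dose weeks out of that one comparison. Neither version makes the pre-dose period typical: exclusion criterion 8 removes subjects with clinically significant laboratory, vital-sign or ECG abnormalities at Screening, and Section 7.1.2 records examination abnormalities found at Screening as medical history. Any comparison kept should therefore be labelled descriptive.
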